Month 4 Session – HH	Education and strategies provided/reinforced and referrals	HH	
Month 7 Session – CHW	Documenting school and family issues	CHW	Month 7 Session
Month 7 Session – HH	Education and strategies provided/reinforced and referrals	HH	
Month 9 Session – CHW	Documenting Empowerment to family	CHW	Month 9 Session
Month 9 Session – HH	Education and strategies provided/reinforced and referrals	HH	
Between Session Log	Track contacts between participants and CHW/HH outside of the four sessions	CHW/HH	Intervention
E-SOC Mailing Log	Track mailing of asthma information	Project coordinator	Quarterly

E3 Changes to study sessions due to COVID-19

Due to COVID-19 (mid-March 2020), we have converted RVA Breathes to a remote program for families. Families are given the option of completing the research and intervention sessions as phone sessions or video sessions through Zoom. If the family chooses Zoom, all privacy and confidentiality protocols will be followed. Control families are emailed or mailed educational materials during the intervention phase. We have developed “contactless” procedures to drop off intervention materials and cash payments at participants’ homes. These procedures include calling the family ahead of time, maintaining a distance of at least 10 feet, wearing a mask, placing items in front of the home, and waiting for retrieval before leaving the area. Intervention materials include pillowcase covers, air purifiers, cleaning products, filters, and supplies for pest removal. These materials will be dropped off after the intervention session.

As we are able to complete follow up sessions remotely with families, we will plan to continue remote follow up sessions with families that have moved out of state. Research staff will conduct these sessions via phone or video depending on family preference. Payments will be made with an e-gift card.

Given the relevance of COVID-19 to participants’ lives and its potential impacts/interactions with the study interventions, we have also added the following items to study questionnaires:

- To the beginning of the data forms used at each intervention session: “How has the COVID-19 pandemic impacted you and your family?”
- To the end of the data forms used at each intervention session: “What did you think of the phone/video session today instead of an in-person visit?”

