Program-specific data will be gathered from CHWs, Healthy Homes, school nurses, and child medical homes. All metrics will be entered directly into REDCap. This information will be used to assess the implementation of the project, including whether short-term outcomes were achieved.

Metrics from home visits. CHWs and Healthy Homes assessors will complete electronic productivity reports regarding their productivity on the study as staff, including time spent on each component of the session, content that was covered, and content that was not (and reason). Information on family questions and barriers described will also be entered in reports. CHWs will also be prompted to ask caregivers a series of paper questionnaires at each visit related to symptoms, asthma control, medication use and changes, healthcare utilization, and missed school days. In their productivity reports, Healthy Homes will note observations of the home environment, as well as document education shared, materials provided to the family, and referrals to MLP-R. Visual observations about the home environment include exterior and interior observations that pertain to the Asthma Environment Checklist from EPA (e.g., standing water, presence of tobacco smoke, mold, pests, or pets).

Metrics from nurses. Nurses will record data on paper forms or in an electronic file if preferred related to interactions with student, any reported health care utilization from student, school absences (for CHW follow-up), and care coordination activity (with family and/or PCP).

Metrics from health systems. Information from health systems (area hospitals) will contain patient identifying information. Data will include information related to units, duration, and frequency of ED visits and hospitalizations due to asthma in the last year.

Metrics from medical homes. CHWs and the project coordinator will document children's visits to their primary care provider or other physician for asthma care. CHWs will ask caregivers to report on any child asthma-related visits to a provider throughout their time in the study; number of visits and reason for visit will be recorded, including whether it was a preventative or an urgent visit. If the child is enrolled in the school intervention group, CHWs or the project coordinator will communicate with the provider's office to ensure that the school has an asthma action plan and medication release form on file at the school.

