
Aim 2: We hypothesize that secondary outcomes (asthma control, symptoms, quality of life) of children in the intervention groups will be superior to those of the control group. These outcomes will be tested using the GLMMs described under Aim 1 utilizing the proper distribution and link functions for the outcome variable examined.

Aim 3: We hypothesize that intervention effects will be mitigated in families with caregivers with lower levels of asthma self-management skills at baseline, as well as in those with higher baseline levels of stress and depressive symptoms. These outcomes will also be tested using the GLMMs described under Aim 1 utilizing the proper distribution and link functions for the outcome variable examined that have been modified by the inclusion of an additional effects measuring caregivers' self-management skills, as well as stress and depressive symptoms. The inclusion of these covariates will allow us to adjust the intervention effects and increase the

generalizability of the intervention effects based upon caregivers' characteristics.

Sample size. From RVA Breathes baseline data, Group 1 children (full intervention: CHW + HH assessors + school) had a 9-month ED visit rate of 2.22 visits. Group 2 (CHW + HH, no school) had a 9-month ED rate of 1.89 visits, and Group 3 (control) had a 9-month ED rate of 1.68. We used recent published rates from a comparable study that considered changes in child asthma-related ED visits from 6 months prior to intervention to 6 months post-intervention (Johnston et al., 2019). In this study, the intervention group went from 2.0/6mo (pre) to 0.55/6mo (post) and the control group went from 1.3/6mo (pre) to 0.85/6mo (post). Thus, the intervention group had a 72% reduction $((2.0-0.55)/2.0 = 0.72)$ and the "control" group had a 35% reduction $((1.3-.85)/1.3 = 0.35)$.

Basing our numbers on these same rates, we would expect the following power estimates with 9-month follow up data: 14% for Groups 1 vs. 2, 97% for Groups 1 vs. 3, and 88% for Groups 2 vs. 3. Using alpha = .0167, we would assume average clusters of 10 in 24 schools for 240 enrolled participants. Allowing for 20% attrition, this would be 300 participants. Moreover, using a Poisson model for analyses, we would use a CVB (between-cluster coefficient of variation) instead of ICC. These analyses would use a CVB for G1 vs. G2 = 0.1331, for G1 vs. G3 = 0.1820, and for G2 vs. G3 = 0.0502.

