Missingness. We will handle missing data in several ways. Health utilization is being reported by caregivers (self-report) and we are also receiving health encounter data from insurers and hospital billing systems. For families that have been lost to follow-up but have not asked to withdraw from the study, we will still receive and use their objective health encounter data. This will limit missingness related to our main outcomes when using encounter data. For self-report data, we will conduct a sensitivity analysis on raw data and examine patterns of missingness. We then will use a pattern-mixture model with multiple imputation from other available timepoints. We can then compare those analyses to analyses using objective health encounter data.

Missing Data and Participant Attrition Strategies:

The primary analysis will follow the approved statistical analysis plan, without any changes for missing data. After fitting this model, missing data patterns will be examined and their patterns will be examined, in particular looking for a monotone missing data pattern indicative of attrition. If, as expected, we find that there is a monotone pattern of missing data (i.e., once an individual misses an observation, they will be missing all subsequent observations), this will provide evidence that the missing completely at random (MCAR) and missing at random (MAR) assumptions may be violated. To examine the impact of monotone missing data, multiple imputation using a pattern-mixture model with control-based imputation will be utilized. We will create 50 imputed datasets for the outcomes and analyze them using the primary analysis model. The results from these 50 analyses will then be combined to derive an overall result. This will allow us to perform a sensitivity analysis to see how much bias the missing data causes.

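### The SAP does not define when a child is observable in encounter data, so an absence of records may be counted as zero events

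*SAP*

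**What the plan says.** The SAP (Aim 1) defines the primary outcome as each child's sum of asthma-related inpatient and ED visits. The endpoint is the change in mean rate from the 9 months before to the 9 months after the programme. The model terms listed are group, time, their interaction, a random school effect, seasonal terms and a COVID-19 indicator. No exposure offset is listed.

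For families lost to follow-up who have not asked to withdraw, the Missingness section says "we will still receive and use their objective health encounter data", and adds: "This will limit missingness related to our main outcomes when using encounter data".

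The protocol (E14) describes the two sources. On hospitals: "Information from health systems (area hospitals) will contain patient identifying information". From insurers it lists the frequency, length and cost of asthma inpatient and ED visits, plus prescriptions and refills. Enrolment or coverage dates are not on the list.

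On missing data the SAP says: "The primary analysis will follow the approved statistical analysis plan, without any changes for missing data". As a sensitivity analysis, "multiple imputation using a pattern-mixture model with control-based imputation will be utilized", with 50 datasets. For self-report there is a separate pattern-mixture imputation, after which: "We can then compare those analyses to analyses using objective health encounter data".

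**The concern.** Encounter files record visits. They do not record that someone was watching and saw none. When events are summed over a file, a child who had no visits and a child who has left the file's reach both give zero, and zero is the best possible value of this outcome.

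The two windows are not equally visible. At entry the child must live in Richmond City and attend a Richmond public school (protocol D2, 2.a), and the caregiver reports the previous 12 months (E4). Nine to 18 months after baseline none of this need still hold, and a family that is out of contact gives no report. Because the endpoint is a before-to-after change, unseen time in the later window looks like improvement. If unseen time differs by arm, the primary contrast is biased.

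**Working it through.** **The plan's own figure.** The SAP's only number on loss is in its Sample size section: "Allowing for 20% attrition, this would be 300 participants". This reproduces: 24 schools × 10 = 240, and 240/(1 − 0.20) = 300. It describes general attrition and is used below only as a reference point.

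**How an unseen child passes through the plan.**
1. The family is lost but not withdrawn, so encounter data are used.
2. The child receives care outside the area hospitals and is no longer covered by a supplying insurer, so neither source holds a record.
3. The sum score over no records is 0.
4. With no offset, that 0 stands for a full 9 months.
5. The imputation acts on missing values, and this value is not recorded as missing.

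**Size.** Let u be the share of an arm's post-period time that is unseen and counted as event-free, with the same event rate in unseen as in seen time. Then:
- observed post/pre ratio = true ratio × (1 − u)
- observed reduction = 1 − true ratio × (1 − u)
- between-arm ratio of rate ratios = true value × (1 − u_active)/(1 − u_control)

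The documents give no value for u. I assume 0% to 30% per arm.

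*Within arms.* The SAP's planning rates give true ratios of 0.55/2.0 = 0.275 (active) and 0.85/1.3 = 0.654 (control).

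| u, both arms | Active reduction | Control reduction | Ratio of rate ratios |
|---|---|---|---|
| 0% | 72.5% | 34.6% | 0.421 |
| 10% | 75.2% | 41.2% | 0.421 |
| 20% | 78.0% | 47.7% | 0.421 |

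Equal loss cancels on the rate-ratio scale. It does not cancel on the absolute scale. With the SAP's baseline rates, the Group 1 minus Group 3 difference in change at u = 0 is 2.22 × 0.725 − 1.68 × 0.346 = 1.03 visits. At u = 20% it is 2.22 × 0.780 − 1.68 × 0.477 = 0.93.

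*Between arms, no true effect.*

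| Unseen, one arm vs other | If the active arm loses more | If control loses more |
|---|---|---|
| 12.5% vs 7.5% | 0.875/0.925 = 0.95 | 1.06 |
| 15% vs 5% | 0.85/0.95 = 0.89 | 1.12 |
| 20% vs 10% | 0.80/0.90 = 0.89 | 1.125 |
| 30% vs 10% | 0.70/0.90 = 0.78 | 1.29 |

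The first two rows average 10% unseen, half of the SAP's 20% attrition. The last averages 20%, as if all attrition were unseen.

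*Type I error.* I used a normal approximation for the log ratio of Poisson rate ratios, with 80 children per arm, a pre-period rate of (2.22 + 1.89 + 1.68)/3 = 1.93, a true ratio of 0.654 in both arms and two-sided alpha 0.0167. The error per comparison is 0.0167 with equal loss, about 0.039 at 20% vs 10%, and about 0.13 at 30% vs 10%. Clustering and overdispersion are ignored; allowing for either would enlarge the standard error and reduce the inflation.

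**The case against.** Several points on the other side stand.

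- A reader might infer that the SAP treats encounter data as complete, or that it scores unseen children as zero. It says neither. Its verb is limit, which concedes some residual missingness, and no scoring rule is written. The zero is what the plan produces by default because it is silent.
- A reader might infer that moving away, or changing insurer, is enough by itself. It is not. A child who moves but stays covered can still appear in claims, and a child who changes insurer but stays local still appears in area-hospital data. Both sources must normally fail together.
- A reader might take the protocol's mention of moves as an expectation that many families will leave. In E3, "we will plan to continue remote follow up sessions with families that have moved out of state" is a retention measure. It gives no rate, and families followed that way still report utilization. It shows only that moves were foreseen.
- The self-report analysis imputes later reports for lost families and is then set beside the encounter analysis, so a large discrepancy might show. That could hint at the problem. It would not correct the primary estimate or identify the children concerned.
- Active families have four home visits of 2 to 2.5 hours while controls receive mailings. That could explain unequal loss of contact, but not unequal moving or loss of coverage. The documents do not establish unequal loss in either direction.
- The 20% attrition may include withdrawals, to whom the encounter-data provision does not apply.

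These points limit how many children are affected and remove any presumption about the direction of bias. They do not supply a definition of observability.

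**Conclusion.** The concern holds as a gap in the definition of the primary outcome. Followed as written, the plan cannot separate a child with no visits from a child nobody could see, and its missing-data provisions do not reach the second case.

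The size depends on shares that the documents do not give. Under the stated assumptions the rate ratio is distorted by roughly 5% to 12% when the arms differ by 5 to 10 percentage points in unseen time, in whichever direction the difference runs. The documents do not support a claim that the bias favours the intervention. With equal loss a log-link group-by-time contrast is unbiased, while the within-arm reductions, and the contrast on the absolute scale, are distorted. If coverage proves nearly complete the effect is negligible, but the plan as it stands collects nothing that would show this.

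**What to change.** In the SAP:

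1. Define a month as observed if any one of these holds: the child was enrolled with an insurer supplying data; the caregiver reported utilization for that month; or the family was documented as living in the area served by the participating hospitals. The third condition matters. Without it, real area-hospital visits by local children who have no supplying insurer would be discarded.
2. Add coverage start and stop dates to the insurer data request, and take last confirmed residence from study contacts.
3. Put log(observed months) in the primary GLMM as an offset, for both the pre and post periods.
4. Treat unobserved months as missing, so that they enter the control-based imputation already planned.
5. Report observed months by arm and period.
6. Keep hospital-recorded events that fall outside observed months for a sensitivity analysis. A visit should not by itself make its month observed, because that would keep months with events and drop those without.

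The cost is SAP wording and one added data field. The stated level of missingness becomes less favourable and intervals slightly wider. The documents do not say whether insurers can supply coverage dates; if they cannot, residence and caregiver report alone can define observed months.
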